10.2 Pregnancy

In case of pregnancy, Investigational Product should be discontinued and the Sponsor informed. Follow-up of the pregnancy will be mandatory until the outcome is available.

10.3 Waiver

Expected cardiovascular efficacy endpoints specified in this trial (primary and secondary efficacy criteria) will not be considered as AEs and will not be subject to expedited regulatory reporting. They will be reported on specific outcome event forms, which should be sent within one (1) working day, by FAX, to the Central Database number.

11. HANDLING OF PATIENT WITHDRAWAL

11.1 List of withdrawal criteria

Occurrence of an outcome event according to the judgment of the Investigator must not be considered as a reason for study drug discontinuation.

Depending on the Investigator's judgment, permanent study drug discontinuation is only clearly justified for an adverse event, when qualifying condition is not present, or when a patient demands to withdraw from study drug treatment, and in such cases the appropriate follow-up until the study end date should still be continued.

Although patients may withdraw from the study drug at any time and for any reason, (or may be withdrawn at the Investigator's decision), patient withdrawal should be avoided as much as possible. If this occurs, every attempt should be made to restart study drug if medically appropriate, whatever the duration of discontinuation. Since the hypothesis being tested in this study is that rimonabant has beneficial cardiovascular effects not necessarily dependent on weight loss, patients should be encouraged to remain on treatment independently of observed weight loss.

The reason for study drug discontinuation will be recorded on the CRF. In any case, appropriate follow-up for efficacy and safety endpoints should be continued.

11.2 Follow-up procedures after withdrawal

Patients who prematurely discontinue study drug are not to be replaced.

All randomized patients must be followed up according to the study flowchart until study end date or death, regardless of whether they discontinued study drug prematurely or not. Any event occurring after early study drug discontinuation will be recorded up through the study end date.

In case of study drug discontinuation (temporary or permanent) due to an adverse event, such patients will be closely monitored until the resolution or stabilization of this adverse event. This may mean that follow-up will continue after the patients have completed the study follow-up. Although data on that adverse event will continue to be captured, even

beyond the last visit, for new efficacy or safety events, only those that occur up through the last visit should be recorded.

In case of written withdrawal of consent (WOC) for follow-up visits, and unless otherwise stated by the patient in the informed consent form, Investigators will be encouraged to get information from the general practitioner, any other physician, or other medical-care provider, in order to follow the medical status of the patients (especially when they withdraw their consent after having experienced an AE/SAE or an efficacy endpoint). Investigators will also be expected to try as much as possible to re-contact those patients at the end of the trial, in order to obtain at least their vital status (dead or alive), as well as their stroke or MI status if possible, and thus avoid lost to follow-up for the efficacy assessment.

For patients considered lost to follow-up, the CRF must be completed up to the last visit performed.

11.3 Consequence

If the drug is stopped prematurely, every attempt should be made to restart it if medically appropriate, whatever the duration of discontinuation.

If the patient withdraws his/her consent for study participation, although in such circumstances he/she may not be obliged to comply with all the protocol visits and phone calls, the Investigators, the study nurses and any other study coordinators are requested to try to obtain as much as possible, the vital status of the patient (dead or alive at a minimum, preferably also stroke or MI status) at study end date. This will be clearly stated in the informed consent form.

Any direct communication with the general practitioner, any other physician or other medical-care provider can be helpful for following the medical status of the patient. This is particularly important if the patient withdraws his consent after experiencing an AE/SAE or an efficacy endpoint since for safety and Regulatory purposes, it is necessary to obtain some information regarding worsening or resolution of the event (especially if this event is considered as to be related to the Investigational Product).

In addition to the need for safety assessment, it is also important to avoid any lost to follow-up patients for the efficacy assessment and meaningful analysis of the study.

12. STUDY PROCEDURES

12.1 Visit schedule

See [Section 1](#) flowchart at the beginning of the protocol.

12.1.1 Pre-screening procedures

Study subjects will be recruited from among participating hospitals, clinics, and diagnostic centers, under the responsibility of a participating Investigator.

Prior to initiation of the recruitment phase, participating Investigators will identify a pool of potential study subjects. Each of these centers will identify potentially eligible patients in advance, by either reviewing past medical records and diagnoses, admissions to coronary care units, admissions to stroke centers, logs of invasive and noninvasive laboratories and relevant surgical procedures, screening in diabetic clinics, referral from other physicians, or other sources of recruitment, to identify those aged 55 or older with increased waist circumference and other risk factors for atherosclerotic cardiovascular or cerebrovascular disease.

12.1.2 Baseline visit

The patient will receive complete information about the study both orally and in writing. Written informed consent must be obtained from the patient prior to any study-specific procedures and prior to randomization.

Compliance with inclusion criteria (listed in Section 7.2) and exclusion criteria (listed in Section 7.3) will be checked on the basis of information collected, and recorded in the CRF.

Key baseline patient characteristics obtained at the randomization visit will be recorded in the CRF, including demographics, vital signs, height, weight, waist circumference, relevant past medical and surgical history, including neurological and psychiatric history, and abnormalities noted on physical exam, including neurological exam.

Medical history, physical examination, laboratory, or instrumental results confirming inclusion and absence of exclusion criteria will be maintained in the patient's file.

12.2 Inclusion procedures

Once all inclusion/exclusion criteria are fulfilled, the patient becomes eligible for randomization and inclusion into the treatment period.

Treatment allocation will be performed as stated above (Section 8.3).

Study medication will be delivered as stated in Section 8.4.

Patients will be counseled to follow a mild hypocaloric diet, to increase their exercise level, and to stop smoking, if they are smokers.

12.3 Description by type of visit

- Baseline visit:
 - informed consent completed and signed
 - check of inclusion and exclusion criteria
 - demographic data
 - medical/surgical history, including neurological and psychiatric history (scripted questions)
 - current medications
 - smoking status

- supine blood pressure and heart rate
 - physical exam, including detailed neurological exam
 - body weight
 - height measurement
 - waist circumference
 - 12-lead ECG
 - hematology (Hb, Ht, WBC-diff, platelets)
 - biochemistry (ALT, AST, ALP, creatinine)
 - urinary pregnancy test (for women of childbearing potential)
 - counseling on diet, exercise, and, if appropriate, smoking cessation
 - call to the IVRS for allocation of a randomized treatment kit number
 - delivery of the corresponding pack of study drug (containing the appropriate amount to allow daily administration until at least the next planned 6 month Treatment visit)
 - first intake of study drug (under medical supervision)
- 1-month Treatment visit (Day 30 ± 7 days)
 - recording of all primary or secondary efficacy endpoints, if any
 - recording of AEs (including neurological and psychiatric AEs), if any
 - supine heart rate and blood pressure
 - check of study drug compliance
 - recording of concomitant medications
- 3-month Treatment visit (Day 90±14 days)
 - recording of all primary and secondary efficacy endpoints, if any
 - recording of AEs (including neurological and psychiatric AEs), if any
 - supine heart rate and blood pressure
 - check of study drug compliance
 - recording of concomitant medications
- 6-month Treatment visit (Day 180±14 days) and subsequent 6 month visits (every 180±14 days)
 - recording of all primary and secondary efficacy endpoints, if any
 - recording of AEs (including neurological and psychiatric AEs), if any
 - check of study drug compliance
 - recording of concomitant medications
 - body weight
 - waist circumference
 - supine heart rate and blood pressure
 - physical exam
 - 12-lead ECG, at penultimate (next to last) visit. The presence of abnormalities, including new pathological (as defined in [Section 9.1.2.1.1](#)) Q waves, will be recorded. If a silent MI is diagnosed in a diabetic patient, an MI outcome form will be completed.
 - hematology (Hb, Ht, WBC-diff, platelets)
 - biochemistry (ALT, AST, ALP, creatinine)

- call to IVRS center for allocation of the second or subsequent treatment kit number
- delivery of the pack of study drug corresponding to treatment kit number, containing the appropriate amount to allow daily administration until at least the next planned 6-month Treatment visit
- Final (end-of-study) visit may occur up to 30 days after but never before the study end date;
 - recording of all primary and secondary efficacy endpoints
 - recording of AEs (including neurological and psychiatric AEs)
 - check of study drug compliance
 - recording of concomitant medications
 - supine blood pressure and heart rate
 - physical exam
 - body weight
 - waist circumference
 - hematology (Hb, Ht, WBC-diff, platelets)
 - biochemistry (ALT, AST, ALP, creatinine)

Every attempt should be made to complete the follow-up visits during the defined window periods.

A final follow-up visit is required for all patients. In the rare cases a final follow-up visit cannot occur within the 30-day timeframe following study end date, any attempt to contact should be recorded on a special contact form, until/unless appropriate information is obtained which will allow completion of final follow-up visit CRF, even after the anticipated timeframe.

After the 6-Month Visit and between subsequent scheduled 6-monthly visits, the Investigator or his designee should contact the patient by phone, ie, at 9 months, 15 months, 21 months and every 6 months thereafter. These regular phone contacts will permit earlier collection of data related to efficacy or safety (including neurological and psychiatric AEs, when clinically relevant observations are made using the scripted questions) and will encourage patient compliance, but they do not aim at making any medical diagnosis by phone. In case an event is identified during a phone call, a subsequent office visit may be required in order to allow appropriate documentation of the efficacy or the safety event. **There is no strict timing for the phone calls. In any case, it is better to call the patient after a delay, than to not call him at all (even in this case, the phone call record page of the CRF should be completed).**

The patient visit schedules will be given by the IVRS as soon as the patient is randomized, so as the Investigator can plan in advance all the necessary appointments with the patient.

12.4 Definition of source data

All the data collected in the CRF come from source documents that are part of the patient dossier. Copies of some of those source documents will be collected after anonymization,

in order to support documentation of outcome events eligible for validation by the Clinical Events Committee, ie:

- for any of those events: a copy of the Hospital Discharge Summary and a clinical description of the event by the Investigator
- for any death: a copy of the death certificate (if applicable and available), autopsy report (if available), 12-lead ECGs (all, including baseline), other relevant reports, and witness description of the death
- for any sudden death: a copy of recent Holter reports (if available) and cardiology notes
- for MI: a copy of the ECG tracings selected from serial ECG and documenting Q-wave MI or non Q-wave MI, biochemical reports (cardiac markers + laboratory reference values) selected from serial tests (eg, peak values) relevant to the diagnosis of MI or re-MI, autopsy report (if available) or other relevant reports (coronary angiography, echocardiography)
- for stroke: CT-scan / MRI report and copy of the films, autopsy report (if available) or other relevant reports (angiography, Doppler sonography...).

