9.1.2.1.1 Myocardial infarction (MI)

Based on American College of Cardiology (ACC) Definitions for Measuring Outcomes (33), three main situations will be considered:

1. Patient who did not undergo recent cardiac intervention (within prior 24 hours):
At least one of the following must be present (biomarker assay must be performed):
 - a) CK-MB elevation ($>2xULN$ in one sample or $>ULN$ in two samples)
 - b) Troponin elevation ($>ULN$ in one sample)
 - c) CK elevation (in absence of a and b, $CK >2xULN$)

AND

At least one of the following (ECG must be performed and documentation should be provided to the Clinical Events Committee):

- Ischemic symptoms within last 24 hours
 - ST depression of at least 0.1 mV or T wave inversion
 - LBBB (new or old) or paced rhythm that obscures assessment of ST
 - ST elevation (new ST elevation in at least two contiguous leads ≥ 0.2 mV in V1, V2, or V3 or ≥ 0.1 mV in other leads)
 - New tall R wave with $R/S \geq 1$ in V1 and $R/S \geq 1.5$ in V2
 - New Q waves ≥ 40 ms in two contiguous leads
2. Patient who underwent recent PCI/CABG (within prior 24 hours):
 - a. Percutaneous coronary intervention (PCI): CK-MB $\geq 3xULN$ (no ECG changes or symptoms required)
 - b. Coronary artery bypass graft (CABG): either CK-MB $\geq 5xULN$ and new Q-waves, as defined above, or CK-MB $\geq 10xULN$ (with or without Q-waves)
 3. If new Q-waves ≥ 40 ms in two contiguous leads occur in a diabetic patient, an MI diagnosis will be established even in the absence of ischemic symptoms and enzyme elevations.

MIIs will be subsequently categorized as Q-wave MI or non Q-wave MI.

All appropriate supportive documentation should be provided to the Clinical Events Committee (see [Appendix 4](#)).

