Appendix 4: The Clinical Events Committee (CEC)

Responsibilities

The Clinical Events Committee is charged with the responsibility for validating all reported primary efficacy outcomes and validating the classification of the cause of all deaths. The event adjudication process will be coordinated by C5.

Members of the Clinical Event Committee will be chosen based on their clinical expertise and language skills. It is expected that most languages will be represented by 2 cardiologists and 2 neurologists. Adjudicators will be trained at a preliminary meeting where study definitions will be reviewed and test cases performed to ensure uniform application of study definitions. Reported events will be adjudicated by at least one committee member. Dossiers of reported events will be prepared and distributed to committee members on a regular basis to ensure that events are adjudicated in a timely fashion. Each committee member will be requested to review the dossiers sent to him/her and acknowledge in writing his/her agreement/disagreement with the investigator's interpretation of events.

Definitions for Validation of Reported Outcome Events

Reported outcome events are all defined in the protocol and only these definitions should be used for adjudication.

- Adjudication of strokes will rely on neurologists in charge of validating such events and their classification as ischemic strokes (IS), hemorrhagic strokes or strokes of unknown cause. Hemorrhagic strokes will be further classified as PICHs and non-PICHs by a Central Neurologist.
- Adjudication of myocardial infarctions (MI) will rely on cardiologists in charge of validating such events and their classification as Q wave MI or non-Q wave MI.
- Adjudication of the cause of death will be performed by the following:
 - neurologists for validation of suspected fatal strokes.
 - cardiologists for all other deaths classified as fatal MI, other CVD, or non-CVD

Fatal strokes, fatal MIs, and other cardiovascular deaths (including unknown causes) will constitute cardiovascular deaths.

Review process for reported efficacy outcome events

- First adjudicator agrees with Investigator's report of outcome event:
 - Agreement acknowledged in writing and filed at C5
 - Event Adjudication database updated accordingly
 - Investigator's report of outcome event accepted
 - Adjudication complete

- First adjudicator disagrees with Investigator's report of outcome event:
 - Disagreement or uncertainty acknowledged in writing

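### Section 12.4 asks for selected rather than complete marker and ECG records for MI, so the Clinical Events Committee is not guaranteed what two parts of the MI definition need

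*Protocol*

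**What the plan says.** Protocol Section 12.4 lists the source documents copied for adjudication. Every event brings "for any of those events: a copy of the Hospital Discharge Summary and a clinical description of the event by the Investigator". For MI the list adds "a copy of the ECG tracings selected from serial ECG and documenting Q-wave MI or non Q-wave MI" and "biochemical reports (cardiac markers + laboratory reference values) selected from serial tests (eg, peak values) relevant to the diagnosis of MI or re-MI". For deaths it asks for "12-lead ECGs (all, including baseline" tracing.

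Section 9.1.2.1.1 defines MI. Without a cardiac intervention in the prior 24 hours (item 1), one marker criterion plus one symptom or ECG criterion is needed. The marker criteria are (a) "CK-MB elevation ($>2xULN$ in one sample or $>ULN$ in two samples"), (b) "Troponin elevation ($>ULN$ in one sample"), or (c) CK above twice the upper limit of normal (ULN), introduced as "CK elevation (in absence of a and b"). After PCI or CABG in the prior 24 hours (item 2), only CK-MB counts: at least 3 times ULN after PCI, and after CABG either at least 5 times with new Q waves or at least 10 times.

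In Appendix 4 each committee member records "his/her agreement/disagreement with the investigator's interpretation of events". If the first adjudicator agrees, adjudication is complete.

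**The concern.** MI is a component of the primary endpoint, which counts only adjudicated events. Adjudication is useful because someone other than the investigator reads the evidence. Section 12.4 lets that evidence be a selection, and describes it by its bearing on the diagnosis: tracings that document the MI, and marker results relevant to it, with peaks as the example. Results that weaken the diagnosis, or that matter only through their timing, may be left out. Whoever compiles the dossier makes that choice, presumably the site, because the copies come from the patient's file. One agreeing vote then ends the review, so no later adjudication step would necessarily bring an omitted result to light.

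The risk runs both ways. An event might be accepted that would fail on the full record, or a true MI that qualifies only through two modest CK-MB elevations might be rejected.

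**Working it through.** **Step 1: set each marker criterion against the minimum dossier.**

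- CK-MB above 2 times ULN in one sample: a peak value settles it.
- CK-MB above ULN in two samples: one peak cannot show it. A second result is needed, and Section 12.4 does not require one.
- Troponin above ULN in one sample: a peak value settles it.
- CK above twice ULN in the absence of (a) and (b): this depends on the reading. If absence means not elevated, the rule reduces to (a), or (b), or CK above twice ULN, and no normal result is needed to accept the event. If it means not measured, the CEC has to know whether CK-MB and troponin were assayed.
- CK-MB thresholds in item 2: a peak value meets the numerical part, if the sample is known to belong under item 2.
- Choice between item 1 and item 2: this turns on timing against the procedure. For example, a peak CK-MB of 2.5 times ULN meets criterion (a) of item 1 but not the 3-times threshold after PCI. A troponin above ULN counts under item 1 and is no criterion under item 2. Section 12.4 does not ask for sampling times.

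Two gaps remain: the two-sample CK-MB arm, and the timing of a sample relative to a PCI or CABG.

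**Step 2: reproduce the plan's own figure (Section 13.2).** Inputs: hazard ratio 0.85, two-sided 5% level, 90% power, equal allocation.

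- Schoenfeld: events = 4 × (1.96 + 1.2816)² / (ln 0.85)² = 1,592. Freedman's formula gives 1,599. The stated figure of about 1,600 reproduces.
- Power with 1,600 events: Φ(|ln 0.85| × √1600 / 2 − 1.96) = Φ(1.290) = 90.2%.

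**Step 3: illustrate the effect of adjudication error.** The protocol gives no error rate, so the rates below are assumptions, taken as equal in both arms.

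*False acceptances.* Let f be the share of counted placebo events that are false, with no treatment effect on them. The hazard ratio becomes 0.85 × (1 − f) + f. With 1,600 events counted:

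- f = 2%: hazard ratio 0.853, power 88.9%.
- f = 5%: hazard ratio 0.8575, power 86.8%.

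If the false events come on top of 1,600 true ones, instead of replacing some of them, power is 89.5% and 88.4%.

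*Wrong rejections.* The hazard ratio stays essentially at 0.85 and only the count falls:

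- 2% missed: 1,600 × 0.98 = 1,568 events, power 89.6%.
- 5% missed: 1,600 × 0.95 = 1,520 events, power 88.6%.

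For scale: 2-5% of 1,600 is 32 to 80 events. If all were MIs, and MI were 40-50% of primary events (an assumption; 640 to 800), that would be between 32/800 = 4% and 80/640 = 12.5% of counted MIs. The upper end is therefore a demanding assumption.

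**The case against.** The strongest reply is that Section 12.4 sets a minimum and forbids nothing. Peak values are an example, reports are in the plural, and a second CK-MB on which the diagnosis depends is plainly relevant to it. Section 9.1.2.1.1 asks for all appropriate supporting documents. The discharge summary, required for every event, can show symptom timing and the date of a procedure. A doubtful adjudicator can record disagreement or uncertainty, which sends the case to a second one. The sponsor clarifies missing documents (Appendix 1), monitoring covers outcome documentation (Section 16.2), and written adjudication guidelines and a quality-assurance manual are planned (Appendix 4). Fatal MIs also fall under the death item, so the ECG contrast concerns nonfatal MI only.

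Most of this stands, and it rules out several stronger readings:

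- That the CEC cannot check MI independently. The documents show only that the needed results are not guaranteed; single-sample criteria can be checked from a peak.
- That the CK criterion admits MIs whose normal CK-MB or troponin the CEC never saw. On the literal reading such an event meets the definition. It is a problem only if absence means not measured.
- That the 24-hour symptom criterion cannot be verified. It is clinical information, which the discharge summary can carry.
- That the protocol gives the selection to the investigator. The sentence is passive and names nobody; the site is an inference.
- That both kinds of error dilute the hazard ratio. Only false acceptances do.

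The reply does not remove the mismatch. Section 12.4 is the only dossier list in the protocol, and Section 9.1.2.1.1 points for documents to Appendix 4, which lists none. The one explicit rule for MI is therefore to select.

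**Conclusion.** The point holds in a limited form. The minimum MI dossier does not guarantee that the CEC can verify the two-sample CK-MB arm, or assign a marker value to item 1 or item 2 when a PCI or CABG is near. The choice of what is sent lies with whoever compiles the dossier, and one adjudicator's agreement ends the process. The death item shows that complete ECG sets were thought feasible.

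No stated figure is wrong. Investigators and the CEC are blinded (Section 8.2, Appendix 5), so errors should be equal between arms, and nothing in the documents suggests bias towards either one. The size cannot be derived from the protocol. The fall in power from 90% to about 89-87% is an illustration that rests on an assumed 2-5% of false events among 1,600 counted; nothing ties that rate to the selection rule. This is a cheap improvement to the evidence for a primary-endpoint component, not the correction of an error that threatens the trial.

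**What to change.** In Section 12.4, replace the selection wording for MI with: all available CK, CK-MB and troponin results of the episode, normal and abnormal, with sampling dates and times and laboratory limits; all ECGs of the episode; and the date and time of any PCI or CABG. Carry the same line into the CEC dossier checklist.

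The cost is one line of text, more copying at sites and slightly thicker dossiers. No new test or assessor is needed, and the definition of MI does not change. The change is best made while events are still being collected, since records not copied at the time may be hard to retrieve later.
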